8.5 Sample Size Calculation

The primary efficacy endpoint of this study is "change from baseline in hepatic fat content at Week 24 as measured by MRI-PDFF".

Sample Size at the Study Initiation:

The sample size was estimated assuming change of 0.8 unit from baseline (treatment difference), standard deviations of 0.3 and 0.4 units, at one-sided 2.5% level of significance (α) and with β level of 0.20 (i.e., 80% power). Using these assumptions, at least 23 completed subjects in each arm (Saroglitazar Magnesium 4 mg and placebo) was required for PP analysis. Considering ~20% dropout rate, around 60 subjects should be enrolled in this proof-of-concept study, with 1:1 treatment allocation ratio i.e. Saroglitazar Magnesium 4 mg (30): placebo (30).

There was no available data with this type of study. In order to understand the disease prevalence and enhance our knowledge of correlation of PCOS and NAFLD, determination of sample size section has been revised.

Revised Sample Size based on current protocol version 5.0:

A sample size of 74 completed participants (37 participants in each treatment arm) will provide 80% power to detect a 4% treatment difference in change from baseline in hepatic fat content at Week 24 between Saroglitazar 4 mg and Placebo using a two-sided 5% level of significance based on a two-sample t-test, assuming change from baseline in hepatic fat content of 9% at Week 24 in Saroglitazar 4 mg treatment arm with a common standard deviation of 0.6.

Document Title:	Statistical Analysis Plan		
Version Number:	Final 1.0	Date:	18Oct2024
Protocol Number:	SARO.17.009	Sponsor Name:	Zydus Therapeutics INC

Assuming a 20% dropout rate at week 24, approximately 90 participants will be randomized in a 1:1 ratio to receive either Saroglitzazar 4 mg (45 Participants) or placebo (45 Participants). The sample size estimation was performed using PASS 14 software.

A total of 12 Participants, 6 Participants in each treatment arm will be included in the pharmacokinetic assessment.

In view of the difficulty and challenges observed in recruitment of study population, it was decided to close recruitment at 60 participants.

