8.6 DETERMINATION OF SAMPLE SIZE

The primary efficacy endpoint of this study is the change from baseline in hepatic fat content at Week 24 as measured by MRI-PDFF. There is no data available on the change from baseline in hepatic fat content measured by MRI-PDFF.

Approved by: [name]	Protocol No. SARO.17.009 Version No.: 5.0
------------------------------------	--

 Zydus Discovery DMCC	CLINICAL TRIAL PROTOCOL Saroglitazar Magnesium – Phase 2A SARO.17.009	Confidential Page 65 of 82
--	---	-------------------------------

A sample size of 74 completed subjects (37 subjects in each treatment arm) will provide 80% power to detect a 4% treatment difference in change from baseline in hepatic fat content at Week 24 between Saroglitazar 4 mg and Placebo using a two-sided 5% level of significance based on a two-sample t-test, assuming change from baseline in hepatic fat content of 9% at Week 24 in Saroglitazar 4 mg treatment arm with a common standard deviation of 0.6.

Assuming a 20% dropout rate at week 24, approximately 90 subjects will be randomized in a 1:1 ratio to receive either Saroglitazar 4 mg (45 subjects) or placebo (45 subjects). Additional subjects may be enrolled if the dropout rate is more than 20%. The sample size estimation was performed using PASS 14 software.

A total of 12 subjects, 6 subjects in each treatment arm will be included in the pharmacokinetic assessment.

Additional patients may be enrolled into the study to ensure the pharmacokinetic assessment is performed on at least 6 completed patients in each treatment arm.

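### SAP 8.5 states 80% power only for 74 completers, gives no power for the 60 at which recruitment closed, and neither of its two calculations reproduces from its printed inputs

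*SAP*

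**What the plan says.** SAP 8.5 sets out two calculations and then a decision.

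- **Calculation at study initiation.** It was made "assuming change of 0.8 unit from baseline (treatment difference), standard deviations of 0.3 and 0.4 units", "at one-sided 2.5% level of significance" and with 80% power. The result is "at least 23 completed subjects in each arm", raised to about 60 enrolled for roughly 20% dropout. The SAP says this was later revised.
- **Calculation under protocol version 5.0**, repeated from Protocol 8.6. It uses a 4% treatment difference, a common SD of 0.6 with no unit, a two-sided 5% two-sample t-test and 80% power. The result is 74 completers, 37 per arm. Protocol 8.6 continues: "Assuming a 20% dropout rate at week 24, approximately 90 subjects will be randomized in a 1:1 ratio".
- **Decision.** Citing recruitment difficulty, the SAP says "it was decided to close recruitment at 60 participants". SAP 7.3 says the same.

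No power, expected number of completers or detectable difference is given for 60. The table of differences from the protocol in SAP section 10 does not list the reduction from 90 to 60.

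**The concern.** The 80% in SAP 8.5 belongs to 74 completers, and the trial can no longer reach that number: even with no loss it has 60. A non-significant result would then be read against a nominal 80% that does not describe the trial as run.

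A reader who tries to work out the power at 60 from the printed inputs cannot do so. The current calculation pairs a difference in percent with an SD that does not appear to be on the same scale. The initial calculation, which does arrive at 60, gives a number per arm that its inputs do not support.

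**Working it through.** **Method.** Two-sample t-test, n per arm, noncentrality δ/(σ√(2/n)), 2n − 2 degrees of freedom, exact noncentral-t power. One-sided 2.5% and two-sided 5% use the same critical value. The normal approximation is n = 2(1.96 + 0.8416)²σ²/δ².

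**1. Current calculation (stated: 37 per arm).** Inputs from Protocol 8.6 and SAP 8.5: difference 4%, SD 0.6, two-sided 5%, 80% power.

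| Reading | δ | σ | n per arm |
|---|---|---|---|
| As printed, same units | 4 | 0.6 | 2 (power 89.1%) |
| 4% as 0.04, SD as printed | 0.04 | 0.6 | 3,532 (normal approximation) |
| Ratio 0.667 | 4 | 6 | 37 (power 80.8%) |
| Ratio 0.667 | 0.4 | 0.6 | 37 (power 80.8%) |

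The stated 37 reproduces exactly, but only at a ratio of 4/6 = 0.667. The documents do not state that ratio; it is inferred from the answer.

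**2. Power at 60 randomised.** With 20% loss, 60 × 0.8 = 48 completers, 24 per arm. With no loss there are 30 per arm. At a standardised difference of 0.667:

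| Completers per arm | Noncentrality 0.667 × √(n/2) | Power | Difference detectable with 80% power if SD is 6 points |
|---|---|---|---|
| 37 (plan) | 2.87 | 80.8% | 4.0 points |
| 30 (60, no loss) | 2.58 | 71.9% | 4.4 points |
| 24 (60, 20% loss) | 2.31 | 61.8% | 5.0 points |

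**3. Effect of baseline adjustment.** The primary model in SAP 9.7.1.3 is ANCOVA with baseline as covariate. If baseline and change correlate at r, the residual SD is σ√(1 − r²). The documents give no r. Assuming 0.3 to 0.5, power is about 66% to 74% at 24 per arm and 76% to 83% at 30 per arm.

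**4. Initial calculation (stated: 23 per arm).** Inputs from SAP 8.5: difference 0.8, SDs 0.3 and 0.4, one-sided 2.5%, 80% power.

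- Root-mean-square SD = √((0.09 + 0.16)/2) = 0.354.
- Normal approximation: 2 × (2.8016)² × 0.125/0.64 = 3.07, so 4 per arm.
- Exact t-test: 4 per arm gives 76.0% and 5 per arm gives 87.8%, so 5 per arm.
- At 23 per arm, power exceeds 99.99%.
- Variants tried (SD 0.4 in both arms, SD 0.7, two-sided 2.5%, 90% power, 0.3 and 0.4 read as variances) give at most 14 per arm.
- With these SDs, a difference of 0.3 gives 23 per arm (80.4%; 22 gives 78.5%). The printed 0.8 may therefore not be the value used, but this is back-solved.

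**The case against.** **The 23 per arm is history.** SAP 8.5 presents that calculation as revised and attributes 60 to recruitment difficulty. It does not say that the sponsor returned to the first calculation, and it claims no power at 60. This stands. A reader might infer that 60 is the originally powered size, or that the error in 23 is why 60 has no power statement; the documents support neither. The statement is missing because recruitment closed early without a recalculation.

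**The step from 74 to 90 might also be called an error.** At 20% loss, 90 yields 72 completers, and 74/0.8 = 92.5. But both documents say approximately 90, and the cost is about one point of power (36 per arm gives 79.7% against 80.8% at 37). It has no bearing on power at 60. Changing 90 to 94 in the SAP would misreport protocol 5.0. It should not be treated as an error.

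**The 62% is conditional.** It needs a ratio that the documents do not state, exactly 20% loss and no covariate adjustment. This also stands. ANCOVA may raise the power, and with no loss and a correlation of 0.5 it would pass 80%. The primary population is per protocol (SAP 8.2, 9.7.1.3), so compliance and deviation exclusions may lower it. A range is needed.

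**Nothing in the analysis changes.** True: endpoint, population, model and decision rule are untouched. The point concerns how the result will be interpreted.

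**Conclusion.** The point holds. The only power stated in the SAP belongs to 74 completers, and the design in force, at 60 randomised, does not deliver it on the plan's own basis of an unadjusted t-test. If the standardised difference is 0.667, power on that basis is about 62% with 20% loss and about 72% with none. If the SD is 6 points, the corresponding detectable differences are about 5.0 and 4.4 points, against the planned 4. Both the ratio and the SD of 6 are inferred from the 37 per arm.

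Two printed calculations do not follow from their inputs. The current one mixes scales (2 per arm in common units, against 37), and any power figure at 60 depends on resolving this. The initial one needs 5 per arm, not 23. These two discrepancies rest on the stated inputs alone and are not sensitive to the method. The second is the less important, since that calculation is superseded.

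**What to change.** In SAP 8.5:

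1. Check the protocol 5.0 calculation against its source output and state the difference and the SD in the same units.
2. Add the expected completers at 60 randomised (48 at 20% loss) and the power or detectable difference as a range over loss, noting that baseline adjustment may raise the power and per-protocol exclusions may lower it. If the ratio of 0.667 is confirmed, the unadjusted range is about 62% to 72%.
3. Correct the initial calculation from its source. If the source is not available, mark the 23 per arm as not reproducible from the stated inputs. In either case, say that it is not the basis for the final size of 60. Do not substitute 0.3 for 0.8 only because it gives 23.
4. Leave the recital of 90 as it is.

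Listing the reduction from 90 to 60 in SAP section 10 would complete the record. The cost is SAP wording only, with no extra patients and no change to the analysis. The downside for the sponsor is a less favourable stated power.

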7.3 Study Population

Participants of PCOS with NAFLD will be recruited for this study.

Number of Participants Planned:

A total 90 participants (including 20% dropouts) was planned to enrolled across USA and Mexico in a ratio of 1:1 to have 45 participants in each treatment arm i.e., Saroglitazar Magnesium 4 mg and placebo.

Six participants in each group are planned for pharmacokinetic assessment therefore a total of 12 participants will be included for pharmacokinetic assessment.

In view of the difficulty and challenges observed in recruitment of study population, it is decided to close recruitment at 60 participants.

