9.7.1.3 Analysis Strategy

Primary analysis will be primarily based on the PP population and analysis, based on mITT population with missing value imputation for primary endpoint will be considered as supportive analyses.

The primary efficacy endpoint in this study is the change in hepatic fat content from baseline following 24 weeks of treatment measured by MRI-PDFF. The change from baseline of hepatic fat will be determined as (Visit 8 [Week 24] value – Baseline value).

The actual values observed and change from baseline values of hepatic fat content will be summarized using the number of non-missing observations (n), mean (Mean), standard deviation (SD), median, minimum (Min) and maximum (Max) by treatment groups for baseline and scheduled all visits (i.e. baseline to Week 24 visits).

To check the mean significance difference between baseline and scheduled visit for Week 24, a paired t-test at 5% level of significance will be used.

Following sample SAS code will be used for paired t-test:

```
proc ttest data=data sides=2 alpha=0.5;
paired BASE*AVAL;
run;
```

Where AVAL: variable with post baseline value; BASE: variable with baseline value.

Document Title:	Statistical Analysis Plan		
Version Number:	Final 1.0	Date:	18Oct2024
Protocol Number:	SARO.17.009	Sponsor Name:	Zydus Therapeutics INC

The primary efficacy endpoint, the change from baseline in hepatic fat content at Week 24 will be analyzed using an analysis of covariance (ANCOVA) model. The model will include change in the hepatic fat content values from baseline as dependent variable, treatment group as a fixed effect and baseline values as a covariate.

The estimate the LS means for treatment groups and its 95% confidence interval, the difference of LS Mean for treatment group (Saroglitzaz magnesium 4 mg – Placebo) and its 95% confidence interval of the difference of LS Mean for treatment group, and p-value to check the significance difference at 5% level of significance will be generated using ANCOVA model.

The following sample SAS code pertains to the ANCOVA analysis:

```
proc mixed data=DATA;
class TRT;
model CHG = BASE TRT/solution;
lsmeans TRT/ stderr pdiff cl alpha=0.05;
ods output diffs = DIFFS lsmeans = LSMEANS;
run;
```

Where, CHG: variable with change from baseline values; BASE: variable with baseline values; TRT: variable with treatment values.

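### Neither printed sample size follows from its printed inputs (37 per arm from 4% and SD 0.6; 23 per arm from 0.8 and SDs 0.3/0.4), and no power or precision is given for the 60 at which recruitment closes

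*SAP*

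**What the plan says.** SAP 8.5 prints two calculations.

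- **At study initiation:** "assuming change of 0.8 unit from baseline (treatment difference), standard deviations of 0.3 and 0.4 units", one-sided 2.5%, 80% power. The result is "at least 23 completed subjects in each arm" and, after about 20% dropout, "around 60 subjects should be enrolled in this proof-of-concept study".
- **Current (protocol version 5.0):** 74 completers, 37 per arm, for 80% power to detect a 4% difference in change in hepatic fat. The test is a two-sample t-test at two-sided 5%, and the active arm is assumed to change by 9%, "in Saroglitazar 4 mg treatment arm with a common standard deviation of 0.6". Allowing 20% dropout, about 90 are to be randomised. Protocol 8.6 gives the same inputs, also "with a common standard deviation of 0.6".

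SAP 8.5 ends by saying that, because of recruitment difficulty, "it was decided to close recruitment at 60 participants". SAP 7.3 repeats this ("it is decided to close recruitment at 60 participants"). Neither section says what 60 participants can detect under the current assumptions. The planned primary analysis is an ANCOVA with "treatment group as a fixed effect and baseline values as a covariate" (SAP 9.7.1.3).

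**The concern.** The current paragraph prints everything needed to check it: difference, SD, test, significance level, power and n. Its difference is either nearly seven times its SD or about one fifteenth of it, and neither is compatible with 37 per arm. The study-initiation paragraph has the same kind of mismatch, with a difference more than twice the average SD.

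The closure makes this more than a historical misprint. The number 60 equals the study-initiation target, so a reader could infer that the trial is back at a design with 80% power. That inference needs the study-initiation calculation to be sound, and it is not. The only current power statement belongs to 74 completers, which 60 randomised cannot supply. SAP 9.7.1.3 declares the study a success or not on a formal test, so a non-significant result cannot be interpreted without knowing which difference 60 participants could have detected.

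**Working it through.** **Method.** For n completers per arm, difference δ and SD σ, power comes from the noncentral t distribution with 2n − 2 degrees of freedom, noncentrality (δ/σ)√(n/2), and the 97.5% t quantile as critical value. One-sided 2.5% gives the same n as two-sided 5% here.

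**1. The plan's 37 per arm** (4%, SD 0.6; SAP 8.5 and protocol 8.6)

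| Reading | δ/σ | n per arm for 80% | Power at 37 |
|---|---|---|---|
| 4 with SD 0.6 | 6.67 | 2 (power 0.891) | about 100% |
| 0.04 with SD 0.6 | 0.067 | 3,533 | about 6% |
| 4% of 9, i.e. 0.36, with SD 0.6 | 0.60 | 45 | – |

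Two other readings also miss: 0.6 as a coefficient of variation of the 9% change (SD 0.6 × 9 = 5.4) gives about 29, and 0.6 as a log-scale SD gives about 17 or 42, depending on whether the placebo change is 5% or 13%.

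**2. What would give 37.** It is the smallest n reaching 80% only when δ/σ lies between about 0.660 and 0.670. Both 4 with SD 6 and 0.4 with SD 0.6 have δ/σ = 0.667 and power 0.808 at 37 (0.797 at 36). A tenfold scale slip is therefore likely, but the documents do not show which figure is wrong.

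**3. The study-initiation 23 per arm** (SAP 8.5). The text names no test, so the t-test is assumed.

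- Pooled SD = √((0.3² + 0.4²)/2) = √0.125 = 0.354, so δ/σ = 0.8/0.354 = 2.26.
- Power is 0.760 at 4 per arm and 0.878 at 5, so n = 5. The Welch form also gives 5.
- At 23 per arm, power exceeds 99.99%.
- 23 would follow from a difference of 0.3 with those SDs (power 0.804), or from 0.8 with a common SD of about 0.93 to 0.95. Neither pair is printed.

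**4. What 60 gives if 37 per arm for 80% was intended.** With 20% dropout, 60 × 0.8 = 48 completers, or 24 per arm; with no dropout, 30 per arm. The SD of 6 points is inferred from step 2, not stated in the plan.

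| | 24 per arm | 30 per arm |
|---|---|---|
| Power at δ/σ = 0.660 | 61.0% | 71.0% |
| Power, 4 points, SD 6 | 61.8% | 71.9% |
| Difference detectable at 80% power, SD 6 | 4.96 points | 4.41 points |
| 95% CI half-width, t × 6 × √(2/n) | 3.49 points | 3.10 points |

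Sensitivity for 4 points at 24 per arm: SD 5 gives 77%, SD 7 gives 49%, SD 8 gives 40%. If instead the printed inputs were right and 37 wrong, power at 24 per arm would be about 100% (4/0.6) or 6% (0.04/0.6).

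**5. Effect of the ANCOVA.** With correlation r between baseline and change, the residual SD is 6√(1 − r²), with 2n − 3 degrees of freedom. The documents give no r. Assumed values of 0.3, 0.5 and 0.6 give 66%, 74% and 81% at 24 per arm, and 76%, 83% and 89% at 30. Simulation at 24 per arm (40,000 trials), which also counts the cost of chance baseline imbalance, gives 65%, 73% and 80%.

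**The case against.** The strongest reply accepts the arithmetic and disputes the weight.

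- **Nothing in the analysis depends on it.** Recruitment closes for feasibility, and correcting an SD alters neither enrolment, the model nor the success rule. This is true, and it is why the remedy is confined to text. It does not make the printed justification correct.
- **The study-initiation paragraph is superseded** and does not appear in protocol 8.6. Also true, and the SAP does not claim that it supports closing at 60. But it stands in the body of the current SAP, and it is the only place where about 60 enrolled is tied to 80% power.
- **A proof-of-concept study owes no power figure at 60**, the shortfall is disclosed, and the analysis will report a 95% confidence interval. Achieved precision will indeed be visible at the end. Even so, the only current power statement describes a design that will not be run, and SAP 9.7.1.3 still applies a pass/fail test.
- **The power figures rest on assumptions.** This stands. SD 6, 24 completers per arm and the correlations are not in the documents, and across them power runs from 40% to 89%. The 61-62% is conditional and is not an estimate of the trial's true power.

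**Conclusion.** The concern holds in all three parts. The current inputs, repeated in both documents, give 2 or 3,533 per arm and not 37. The study-initiation inputs give 5 per arm and not 23. No power, detectable difference or interval width is stated for 60 under the current assumptions.

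Taking 37 per arm at 80% as the intended design, closing at 60 lowers t-test power to about 61-62% with the plan's 20% dropout, or 71-72% with none. With an SD of 6 points, the difference detectable at 80% power with 24 per arm is about 5.0 points, above the planned 4. The ANCOVA would recover some of this, and at a correlation near 0.6 it would bring power back to about 80%. No planned estimate, test or decision rule is affected. Left as it is, the error would carry into the study report.

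**What to change.** 1. Retrieve the PASS output and correct the difference and SD in SAP 8.5 and protocol 8.6 on one scale, with units. Say whether the 4%, the 9% and the SD are absolute PDFF percentage points or relative change; the endpoint is the simple difference, Week 24 minus baseline. If no further protocol amendment is planned, record the correction in the SAP's table of differences from the protocol (section 10).
2. Correct or explain the study-initiation inputs (0.8; 0.3 and 0.4) from the same source, and name the test.
3. Add to SAP 8.5 the power, the detectable difference and the expected 95% CI half-width for 60 randomised (about 48 completers at 20% dropout). State the SD, dropout and test used, and the baseline-change correlation if the figure is for the ANCOVA.
4. Mark the statement of 80% power, 74 completers and 90 randomised as the superseded plan. SAP 7.1 and 8.5 still say that about 90 will be randomised.

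The cost is text only. The stated power becomes less favourable, but no patients are added and the analysis is unchanged.

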8.6 Interim Analysis

No Interim Analysis has been planned for this study.

8.7 Statistical Software

All statistical analyses will be performed using SAS® Version 9.4 or higher [SAS Institute Inc., USA]. The sample size estimation was performed using PASS 14 software.

Document Title:	Statistical Analysis Plan		
Version Number:	Final 1.0	Date:	18Oct2024
Protocol Number:	SARO.17.009	Sponsor Name:	Zydus Therapeutics INC

9 Statistical Analyses

9.1 Participant Disposition

Participant disposition table will be presented by treatment group and by overall. The following summaries will be included in the disposition table: total number of participants screened in the study, number of participants who failed screening, number of participants discontinued before randomization (apart from screen failure), number of participants randomized, number of participants treated (i.e., administered with treatment), number of participants who completed the study (Week 24 treatment assessment), and number of participants who discontinued from the study with primary reason for discontinuation. Percentages of participants will be calculated based on the number of participants who are randomized. All screened participants (i.e., who have provided informed consent) will be used for participants disposition summary table.

Summary of participants for each investigational site will also be provided by treatment using frequency count and percentage (%) for safety population.

Participants who are consented to participate in the study, by-participants data listing for all available data information will be provided for participant disposition.

9.2 Analysis Populations

The analysis population will be defined and the assignment of participants to each of the analysis population will be finalized before data base lock (DBL). The complete list of participants excluded from any of the analysis populations as well as the reason(s) for exclusion will be presented. Analysis population, that is number (n) and percentage (%) of participants included in each analysis population, will be presented by treatment group and by overall, for all centers/countries combined as appropriate for the study design. A participant may have more than one reason for exclusion from a given analysis population and all percentages will be calculated relative to the number of participants randomized. All randomized participants will be used for analysis populations summary table.

